8.3.4. Clinical Safety Laboratory Assessments

See Appendix 2 for the list of clinical safety laboratory tests to be performed and the SoA for the timing and frequency. All protocol-required laboratory assessments, as defined in Appendix 2, must be conducted in accordance with the laboratory manual and the SoA. Unscheduled clinical laboratory measurements may be obtained at any time during the study to assess any perceived safety issues.

The investigator must review the laboratory report, document this review, and record any clinically significant changes occurring during the study in the AE section of the CRF. Clinically significant abnormal laboratory test findings are those that are not associated with the underlying disease, unless judged by the investigator to be more severe than expected for the participant's condition.

All laboratory tests with values considered clinically significant and abnormal during participation in the study or within 90 days after the last dose of study intervention should be repeated until the values return to normal or baseline or are no longer considered clinically significant by the investigator or study medical monitor.

If such values do not return to normal/baseline within a period of time judged reasonable by the investigator, the etiology should be identified and the sponsor notified.

See Appendix 6 for suggested actions and follow-up assessments in the event of potential DILI.

See Appendix 7 for instructions for laboratory testing to monitor kidney function and reporting laboratory test abnormalities.

Participants may undergo random urine drug testing at the discretion of the investigator. Drug testing results conducted prior to dosing must be in alignment with Section 5.2 Exclusion Criterion 10 for participants to receive study intervention.

8.3.5. COVID-19 Testing

The testing for COVID-19 will be performed as per SoA and may be performed at each outpatient visit per local site regulations. For participants admitted for CRU confinement, a subsequent COVID-19 test may be performed per local site procedures or if they develop COVID-19 like symptoms. Testing may be completed per local site practice.

8.3.6. Pregnancy Testing

A serum pregnancy test is required at screening. Following screening, pregnancy tests may be urine or serum tests, and must have a sensitivity of at least 25 mIU/mL. Pregnancy tests will be performed in WOCBP at the times listed in the SoA. Following a negative pregnancy test result at screening, appropriate contraception must be commenced and a second negative pregnancy test result will be required at the baseline visit prior to the participant's receiving the study intervention. Pregnancy tests will also be done whenever 1 menstrual cycle is missed during the active treatment period (or when potential pregnancy is otherwise suspected) and at the end of the study. Pregnancy tests may also be repeated if requested by IRBs/ECs or if required by local regulations. If a urine test cannot be confirmed as negative (eg, an ambiguous result), a serum pregnancy test is required. In such cases, the participant must be excluded if the serum pregnancy result is positive.

8.3.6.1. At-Home Pregnancy Testing

If a participant requiring pregnancy testing cannot visit a local laboratory, a home urine pregnancy testing kit with a sensitivity of at least 25 mIU/mL may be used by the participant to perform the test at home, if compliant with local regulatory requirements. The pregnancy test outcome should be documented in the participant's source documents/medical records and relevant data recorded on the CRF. Confirm that the participant is adhering to the contraception method(s) required in the protocol.

8.3.7. Infusion and Injection Site Reaction and Anaphylaxis Assessment

Participants will be monitored for signs of any infusion or injection site reactions, including but not limited to erythema, swelling, bruising, pain, or pruritus at times specified in the SoA.

Any signs or symptoms related to either an infusion or injection site reaction should be treated according to the investigator's standard of care and reported as AEs. All anaphylactic reactions will be assessed by the Pfizer clinical team according to Sampson's criteria (Appendix 9).

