6.4. Blinding

This is an double-blind (sponsor-unblinded) study.

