6.4.3. Blinding of the Sponsor

Sponsor staff not directly involved in the conduct of the study may be unblinded to participants' assigned study intervention as needed to support study activities.

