6.4.4. Breaking the Blind

The method for breaking the blind in this study will be manual. A sealed envelope that contains the study intervention assignment(s) for each participant will be provided to the investigator. The sealed envelope will be retained by the investigator (or representative) in a secured area. In case of an emergency, the investigator has the sole responsibility for determining if unblinding of a participant's treatment assignment is warranted. Participant safety must always be the first consideration in making such a determination. If the investigator decides that unblinding is warranted, the investigator should make every effort to contact the study medical monitor prior to unblinding a participant's treatment assignment unless this could delay further management of the participant. If a participant's treatment assignment is unblinded, the sponsor must be notified within 24 hours after breaking the blind. When the blinding code is broken, the reason must be fully documented and entered on the CRF/DCT.

Once the study is complete, all envelopes (sealed and opened) must be inventoried and retained until authorization for destruction has been provided.

Blood specimens will be obtained from all participants for PK analysis to maintain the study blind at the investigator site. Only the investigator site staff and blinded study monitor, if assigned, will be blinded to study treatment. Other Pfizer personnel will be unblinded to participant treatments in order to permit real-time interpretation of the safety and PK data; and provide information necessary to potentially alter the dose-escalation sequence. The blinded study monitor, if assigned, will remain blinded to treatment until all monitoring for the study has been completed. Specimens from participants randomized to placebo will not be routinely analyzed. To minimize the potential for bias, treatment randomization information will be kept confidential by Pfizer unblinded personnel and will not be released to the blinded investigator or blinded investigator site personnel until the study database has been locked or the investigator requests unblinding for safety reasons.

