#### 6.1.2. Immune-based AEs

Immune-based adverse events will be summarized by visits. If ADA results are available, immune-based adverse events may be summarized by categories of ADA results (for example, by ADA positive, negative and not-tested categories). Immune-based adverse events will include ISR and IRR, and clinically evaluated results of anaphylaxis based on the Sampson's Criteria, and AEs based on the Anaphylactic Reaction Standardised MedDRA Query (SMQ), Angioedema SMQ, Hypersensitivity SMQ, cytokine storm, and delayed immune response.

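### Anaphylaxis is classified against Sampson's criteria only by the sponsor's unblinded clinical team; a blinded classification should be recorded first and tabulated

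*Protocol*

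**What the plan says.** On the assessment, Protocol Section 8.3.7 has infusion and injection site reactions reported as adverse events, and then adds: "All anaphylactic reactions will be assessed by the Pfizer clinical team according to Sampson's criteria". The risk table in Section 2.3.1 also calls for Sampson's criteria but names no assessor. Appendix 9 prints the criteria.

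On blinding, Section 6.4 labels the trial: "This is an double-blind (sponsor-unblinded) study". Section 6.4.2 blinds investigators and the staff who administer treatment. Section 6.4.3 reads: "Sponsor staff not directly involved in the conduct of the study may be unblinded to participants' assigned study intervention as needed to support study activities". Section 6.4.4 reads: "Only the investigator site staff and blinded study monitor, if assigned, will be blinded to study treatment", and continues: "Other Pfizer personnel will be unblinded to participant treatments in order to permit real-time interpretation of the safety and PK data".

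On reporting, SAP Section 6.1.2 says: "Immune-based adverse events will include ISR and IRR, and clinically evaluated results of anaphylaxis based on the Sampson's Criteria". The basis of the summary is given as: "Immune-based adverse events will be summarized by visits", with an optional split by ADA result.

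Neither document provides a blinded Sampson classification, a blinded adjudicator or masked case material. Protocol Section 10.1.5.1 states that there is no external data monitoring committee.

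**The concern.** Reactions of this kind are the first potential risk listed in Protocol Section 2.3.1, and Section 4.2 justifies the blinded, placebo-controlled design as a way to limit bias and give a reference for safety. If the only formal classification of anaphylaxis is made by people who know the arm, two participants with the same signs could be classified differently because one received antibody and the other placebo. The shift could go either way: a borderline case on active drug could be counted more readily, or explained away. With very few events expected to carry the message, the reported count should be one that a reader can accept as made without knowledge of treatment.

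**Working it through.** **Step 1. Is the assessor unblinded?** Section 8.3.7 names the sponsor's clinical team. Section 6.4.4 lists the blinded parties exhaustively: site staff and, if assigned, a blinded monitor. The clinical team is neither, so it falls among the other sponsor personnel, who are unblinded.

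**Step 2. Do the blinding sections agree?** No.

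| Section | Sponsor staff covered | Status |
|---|---|---|
| 6.4.3 | Those outside the direct conduct of the study | May be unblinded, as needed |
| 6.4.4 | All except an assigned blinded monitor | Will be unblinded |

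Under 6.4.3 alone the clinical team's status is unclear. Under 6.4.4 it is unblinded. Neither section secures a blind classification.

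**Step 3. What is already done blind?** Section 8.4 makes the investigator and designees responsible for detecting and recording adverse events. Appendix 3 (Section 10.3.3) has the investigator seek a diagnosis, grade intensity and judge causality. Section 6.4.2 keeps investigators blinded. Case finding and diagnosis are therefore blind; the Sampson step comes afterwards.

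**Step 4. Where can arm knowledge enter Appendix 9?**

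| Criterion | Content | Allergen element |
|---|---|---|
| 1 | Acute skin or mucosal signs, plus respiratory compromise or reduced BP/end-organ symptoms | None |
| 2 | Two or more of four sign groups (skin/mucosal, respiratory, BP, gastrointestinal) soon after exposure | Likely allergen |
| 3 | Reduced BP after exposure | Known allergen |

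Four sign groups form 4 × 3 / 2 = 6 pairs. Two pairs (skin with respiratory, skin with BP) can meet criterion 1 with no allergen judgement. The other 6 − 2 = 4 pairs (skin with gastrointestinal, respiratory with BP, respiratory with gastrointestinal, BP with gastrointestinal) can qualify only through criterion 2 or 3. There, the classification turns on whether the administered product counts as an allergen, and that is the judgement that knowing drug or placebo informs. This shows where the exposure lies, not how often such presentations occur.

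**Step 5. Scale of one classification.** Cohort sizes come from Sections 4.1.1 and 4.1.2.

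- Cohorts 1-5: active 2 + 2 + 4 + 6 + 6 = 20; placebo 2 × 5 = 10; total 30.
- All eight cohorts: active 20 + 6 + 6 + 4 = 36; placebo 10 + 2 + 2 + 1 = 15; total 51.

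Both totals reproduce Section 9.5. One event is 100/n percentage points of its group:

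| Active group | n | 100/n |
|---|---|---|
| Cohorts 1 and 2 | 2 | 50.0 |
| Cohorts 3 and 8 | 4 | 25.0 |
| Cohorts 4-7 | 6 | 16.7 |
| Pooled, Cohorts 1-5 | 20 | 5.0 |
| Pooled, all cohorts | 36 | 2.8 |

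**Step 6. Can the bias be sized?** That would need the rate of suspected reactions and the probability that arm knowledge changes a classification. The documents give neither. No error rate is involved either, because Protocol Section 9.1 and SAP Section 5.1 rule out hypothesis testing.

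**The case against.** The strongest reply is that sponsor access is declared and has a purpose. The title calls the study sponsor-open, Section 6.4 repeats it, and Section 9.4 reserves unblinded sponsor review. The stopping rules in Section 6.6.1 count events in participants on active drug, which requires knowing the arm. A reader might infer that the double blind is broken, or that the safety comparison as a whole is unblinded. The documents do not support that: participants and investigators stay blinded, and the primary endpoints come from site-recorded data.

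A reader might also infer that the blinded investigator plays no part in identifying anaphylaxis. Section 8.3.7 indeed gives the investigator no Sampson determination, but Appendix 3 requires a diagnosis, and an anaphylaxis so recorded enters the treatment-emergent event tables whatever the sponsor concludes. SAP Section 6.1.1 removes only injection site and infusion related reaction categories from ordinary adverse event reporting. SAP Section 6.1.2 also uses the Anaphylactic Reaction, Angioedema and Hypersensitivity queries, which draw on reported events. The Sampson result is not an endpoint in its own right, and Protocol Section 8.4.8 lists no events of special interest.

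Finally, SAP Section 6.1.2 specifies summaries by visit and possibly by ADA category; it does not state an arm comparison for this item. The safety set is analysed by product received (SAP Section 4), so a comparison by arm is a natural reading, but it remains an inference.

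All of this stands as a limit on weight. None of it supplies a blinded Sampson classification, and the conflict between Sections 6.4.3 and 6.4.4 is untouched.

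**Conclusion.** The point holds in a limited form. A summarized safety classification is assigned to assessors whom Section 6.4.4 leaves unblinded, with no blinded counterpart. The exposure is confined to that secondary step, chiefly the allergen elements of criteria 2 and 3.

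The percentages in the working should not be read as bias. They are 1/n and would apply to any single event of any kind. Nor are all 51 participants affected: only reported anaphylactic reactions are classified.

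The conclusion rests on three assumptions: that Section 6.4.4, the more explicit text, governs over 6.4.3; that the clinical team belongs to the sponsor personnel it describes; and that the evaluated result in SAP Section 6.1.2, which names no assessor, is the assessment made under Section 8.3.7. On that footing this is a worthwhile, inexpensive improvement to a descriptive phase 1 plan, not a defect that undermines it.

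**What to change.** 1. **Protocol Section 8.3.7.** For each suspected anaphylactic reaction, the blinded investigator records on the CRF which Appendix 9 criterion, if any, is met, before sponsor review. The sponsor's assessment is kept as a second, separately labelled classification.
2. **SAP Section 6.1.2.** Tabulate the blinded investigator's classification by treatment group, and list every case in which the sponsor's classification differs.
3. **Protocol Sections 6.4.3 and 6.4.4.** Reconcile them so that one statement says which sponsor staff are unblinded, and state the status of the clinical team that applies Sampson's criteria.

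The cost is one CRF item and short wording changes. No visits, procedures or staff are added, and unblinded sponsor review for dose escalation is unaffected. The downside is that the two classifications may differ, and both must then be shown.

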8.4. Adverse Events, Serious Adverse Events, and Other Safety Reporting

The definitions of an AE and an SAE can be found in Appendix 3.

AEs may arise from symptoms or other complaints reported to the investigator by the participant (or, when appropriate, by a caregiver, surrogate, or the participant's legally authorized representative), or they may arise from clinical findings of the investigator or other healthcare providers (clinical signs, test results, etc).

The investigator and any qualified designees are responsible for detecting, documenting, and recording events that meet the definition of an AE or SAE and remain responsible to pursue and obtain adequate information both to determine the outcome and to assess whether the event meets the criteria for classification as an SAE or caused the participant to discontinue the study intervention (see Section 7.1).

During the active collection period as described in Section 8.4.1, each participant will be questioned about the occurrence of AEs in a nonleading manner.

In addition, the investigator may be requested by Pfizer Safety to obtain specific follow-up information in an expedited fashion.

8.4.1. Time Period and Frequency for Collecting AE and SAE Information

The time period for actively eliciting and collecting AEs and SAEs ("active collection period") for each participant begins from the time the participant provides informed consent, which is obtained before undergoing any study -related procedure and/or receiving study intervention), through and including a minimum of approximately 5 half-lives or until their exposures are below LLOQ after the last administration of the study intervention.

Follow-up by the investigator continues throughout the active collection period and until the AE or SAE or its sequelae resolve or stabilize at a level acceptable to the investigator.

When a clinically important AE remains ongoing at the end of the active collection period, follow-up by the investigator continues until the AE or SAE or its sequelae resolve or stabilize at a level acceptable to the investigator and Pfizer concurs with that assessment.

For participants who are screen failures, the active collection period ends when screen failure status is determined.

If the participant withdraws from the study and also withdraws consent for the collection of future information, the active collection period ends when consent is withdrawn.

If a participant permanently discontinues or temporarily discontinues study intervention because of an AE or SAE, the AE or SAE must be recorded on the CRF and the SAE reported using the CT SAE Report Form.

Investigators are not obligated to actively seek information on AEs or SAEs after the participant has concluded study participation. However, if the investigator learns of any SAE, including a death, at any time after a participant has completed the study, and they consider the event to be reasonably related to the study intervention, the investigator must promptly report the SAE to Pfizer using the CT SAE Report Form.

8.4.1.1. Reporting SAEs to Pfizer Safety

All SAEs occurring in a participant during the active collection period as described in Section 8.4.1 are reported to Pfizer Safety on the CT SAE Report Form immediately upon awareness and under no circumstance should this exceed 24 hours, as indicated in Appendix 3. The investigator will submit any updated SAE data to the sponsor within 24 hours of its being available.

8.4.1.2. Recording Nonserious Aes and SAEs on the CRF

All nonserious AEs and SAEs occurring in a participant during the active collection period, which begins after obtaining informed consent as described in Section 8.4.1, will be recorded on the AE section of the CRF.

The investigator is to record on the CRF all directly observed and all spontaneously reported AEs and SAEs reported by the participant.

As part of ongoing safety reviews conducted by the sponsor, any nonserious AE that is determined by the sponsor to be serious will be reported by the sponsor as an SAE. To assist in the determination of case seriousness, further information may be requested from the investigator to provide clarity and understanding of the event in the context of the clinical study.

8.4.2. Method of Detecting AEs and SAEs

The method of recording, evaluating, and assessing causality of AEs and SAEs and the procedures for completing and transmitting SAE reports are provided in Appendix 3.

Care will be taken not to introduce bias when detecting AEs and/or SAEs. Open-ended and nonleading verbal questioning of the participant is the preferred method to inquire about AE occurrences.

8.4.3. Follow-Up of AEs and SAEs

After the initial AE or SAE report, the investigator is required to proactively follow each participant at subsequent visits/contacts. For each event, the investigator must pursue and obtain adequate information until resolution, stabilization, the event is otherwise explained, or the participant is lost to follow-up (as defined in Section 7.3).

In general, follow-up information will include a description of the event in sufficient detail to allow for a complete medical assessment of the case and independent determination of possible causality. Any information relevant to the event, such as concomitant medications and illnesses, must be provided. In the case of a participant death, a summary of available autopsy findings must be submitted as soon as possible to Pfizer Safety.

Further information on follow-up procedures is provided in Appendix 3.

8.4.4. Regulatory Reporting Requirements for SAEs

Prompt notification by the investigator to the sponsor of an SAE is essential so that legal obligations and ethical responsibilities toward the safety of participants and the safety of a study intervention under clinical investigation are met.

The sponsor has a legal responsibility to notify both the local regulatory authority and other regulatory agencies about the safety of a study intervention under clinical investigation. The sponsor will comply with country-specific regulatory requirements relating to safety reporting to the regulatory authority, IRBs/ECs, and investigators.

Investigator safety reports must be prepared for SUSARs according to local regulatory requirements and sponsor policy and forwarded to investigators as necessary.

An investigator who receives SUSARs or other specific safety information (eg, summary or listing of SAEs) from the sponsor will review and then file it along with the SRSD(s) for the study and will notify the IRB/EC, if appropriate according to local requirements.

8.4.5. Environmental Exposure, Exposure During Pregnancy or Breastfeeding, and Occupational Exposure

Environmental exposure, occurs when a person not enrolled in the study as a participant receives unplanned direct contact with or exposure to the study intervention. Such exposure may or may not lead to the occurrence of an AE or SAE. Persons at risk for environmental exposure include healthcare providers, family members, and others who may be exposed. An environmental exposure may include EDP, EDB, and occupational exposure.

Any such exposures to the study intervention under study are reportable to Pfizer Safety within 24 hours of investigator awareness.

8.4.5.1. Exposure During Pregnancy

An EDP occurs if:

- A female participant is found to be pregnant while receiving or after discontinuing study intervention.
- A male participant who is receiving or has discontinued study intervention inseminates a female partner.

- A female nonparticipant is found to be pregnant while being exposed or having been exposed to study intervention because of environmental exposure. Below are examples of environmental EDP:
 - A female family member or healthcare provider reports that she is pregnant after having been exposed to the study intervention by ingestion, inhalation, or skin contact.
 - A male family member or healthcare provider who has been exposed to the study intervention by ingestion, inhalation, or skin contact then inseminates his female partner prior to or around the time of conception.

The investigator must report EDP to Pfizer Safety within 24 hours of the investigator's awareness, irrespective of whether an SAE has occurred. The initial information submitted should include the anticipated date of delivery (see below for information related to termination of pregnancy).

- If EDP occurs in a participant/participant's partner, the investigator must report this
 information to Pfizer Safety on the CT SAE Report Form and an EDP Supplemental
 Form, regardless of whether an SAE has occurred. Details of the pregnancy will be
 collected after the start of study intervention and until at least 5 terminal half-lives
 after the last dose.
- If EDP occurs in the setting of environmental exposure, the investigator must report
 information to Pfizer Safety using the CT SAE Report Form and EDP Supplemental
 Form. Since the exposure information does not pertain to the participant enrolled in
 the study, the information is not recorded on a CRF; however, a copy of the
 completed CT SAE Report Form is maintained in the investigator site file.

Follow-up is conducted to obtain general information on the pregnancy and its outcome for all EDP reports with an unknown outcome. The investigator will follow the pregnancy until completion (or until pregnancy termination) and notify Pfizer Safety of the outcome as a follow-up to the initial EDP Supplemental Form. In the case of a live birth, the structural integrity of the neonate can be assessed at the time of birth. In the event of a termination, the reason(s) for termination should be specified and, if clinically possible, the structural integrity of the terminated fetus should be assessed by gross visual inspection (unless preprocedure test findings are conclusive for a congenital anomaly and the findings are reported).

Abnormal pregnancy outcomes are considered SAEs. If the outcome of the pregnancy meets the criteria for an SAE (ie, ectopic pregnancy, spontaneous abortion, intrauterine fetal demise, neonatal death, or congenital anomaly in a live-born baby, a terminated fetus, an intrauterine fetal demise, or a neonatal death), the investigator should follow the procedures

for reporting SAEs. Additional information about pregnancy outcomes that are reported to Pfizer Safety as SAEs follows:

- Spontaneous abortion including miscarriage and missed abortion should be reported as an SAE;
- Neonatal deaths that occur within 1 month of birth should be reported, without regard
 to causality, as SAEs. In addition, infant deaths after 1 month should be reported as
 SAEs when the investigator assesses the infant death as related or possibly related to
 exposure to the study intervention.

Additional information regarding the EDP may be requested by the sponsor. Further follow-up of birth outcomes will be handled on a case-by-case basis (eg, follow-up on preterm infants to identify developmental delays). In the case of paternal exposure, the investigator will provide the participant with the Pregnant Partner Release of Information Form to deliver to his partner. The investigator must document in the source documents that the participant was given the Pregnant Partner Release of Information Form to provide to his partner.

